6.8 End of Trial (EOT) Visit

EOT assessments will be performed at the subject's last scheduled visit. If the EOT visit cannot be scheduled on the same day as the last scheduled visit, it can be done the following day. In the case of premature discontinuation from the study, an EOT visit will be completed within 2 weeks after the subject's last scheduled visit.

A physical examination will be done and vital signs will be recorded. The following laboratory tests will be performed by a central laboratory (no AMH will be drawn):

- Serum chemistry: non-fasting glucose, blood urea nitrogen, creatinine, potassium, sodium, chloride, calcium, aspartate aminotransferase, alanine aminotransferase, and gamma-glutamyl transferase.
- Hematology: red blood cell count, white blood cell count, hematocrit, hemoglobin, platelet count, and differential count.

Adverse events and concomitant medications will be assessed and documented and drug accountability will be performed.

6.9 Pregnancy Follow-Up

After confirmation of ongoing pregnancy in the fresh cycle or the 6-month post-treatment frozen-thawed blastocyst transfer cycle, the site will be required to collect delivery information (live birth and neonatal health). The follow-up will be conducted by the study center via telephone or mail and recorded in the eCRF. The site will also document miscarriage/pregnancy loss (spontaneous and/or induced), date of live birth, number of deliveries, gestational age at delivery, birth weight at deliveries, gender, and congenital anomalies/birth defects. Live birth rate after the fresh cycle and

Trial Code: 000205

Date: 10 Dec 2015

E-Protocol Amendment-19588; Ver. 1.0

Supersedes: 28 October 2015

Page 36 of 69

cumulative live birth rate after fresh and 6-month post-treatment frozen-thawed transfer cycles will be evaluated as part of the pregnancy follow-up.

Date: 10 Dec 2015 E-Protocol Amendment-19588; Ver. 1.0 Supersedes: 28 October 2015 Page 37 of 69

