Post-trial follow-up extends to collection of delivery information (live birth and neonatal health to include APGAR scores, birth weight, gestational age at birth, presence of congenital anomaly/birth defect, and cause of neonatal death, if applicable), which will be collected for all subjects with an ongoing pregnancy in the fresh cycle or the 6-month post-randomization frozen-thawed blastocyst transfer cycles. Live birth rate after the fresh cycle and cumulative live birth rate after fresh and 6-month post-randomization frozen-thawed blastocyst transfer cycles will be evaluated as part of the post-trial follow-up.

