6.7 Visits 7, 8, and 9 - Pregnancy Monitoring

- Visit 7: All subjects will be required to return to the clinic approximately 10-14 days after blastocyst transfer for β-hCG assessment. If the first serum β-hCG is positive, a second confirmatory test will be performed approximately 2 days later. If the pregnancy test is negative, ENDOMETRIN[®] will be discontinued and EOT procedures completed. If conflicting results are obtained in the first 2 tests, a third test will be performed 2 days after the second test. If a positive β-hCG is confirmed, ENDOMETRIN [®] will continue up to 10 weeks from the time it was initiated until the EOT Visit.
- **Visit 8**: Subjects who are pregnant will return to the clinic 4-5 weeks after blastocyst transfer for clinical pregnancy assessment (TVUS showing at least 1 intrauterine gestational sac with fetal heartbeat).

Trial Code: 000205

Date: 10 Dec 2015

E-Protocol Amendment-19588; Ver. 1.0

Supersedes: 28 October 2015

Page 35 of 69

• **Visit 9:** Subjects with clinical pregnancy will return to the clinic 8-9 weeks after blastocyst transfer for assessment of ongoing pregnancy (presence of at least 1 intrauterine pregnancy with a viable fetus with a detectable fetal heartbeat).

An End of Trial (EOT) Visit will be scheduled or completed for non-pregnant subjects and the information will be documented in the eCRF.

Non-pregnant subjects: Subjects without 2 positive β -hCG tests, clinical pregnancy, or ongoing pregnancy in the fresh cycle, may undergo a single frozen blastocyst transfer within 6 months of each subject's date of randomization. The PGS results can be used to select the euploid blastocyst for frozen transfer. Frozen-thawed blastocyst transfer cycle data will be collected, including blastocyst transfer information (endometrial thickness and echogenicity, grade of blastocyst, ploidy of blastocyst, presence of blood, or mucus within catheter tip), β -hCG serum results, clinical pregnancy, and ongoing pregnancy for the first frozen blastocyst transfer cycle following negative pregnancy.

Subjects may also return to the study center for regularly scheduled clinic visits as required per study center standard of care. The data collected during these visits will not be documented in the eCRF unless it is new or is a change in concomitant medications, pregnancy, or AEs.

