7 TRIAL ASSESSMENTS

7.1 Assessments Related to Endpoints

7.1.1 Pregnancy Tests and Pregnancy Monitoring

Positive β -hCG will be based on the detection of 2 positive β -hCG tests in serum via central laboratory. β -hCG pregnancy tests will be performed for all subjects 10-14 days after blastocyst transfer, with a second test approximately 2 days later, if the first test is positive. If conflicting results are obtained in the first 2 tests, a third test will be performed 2 days after the second test. Subjects who achieve pregnancy (2 positive serum pregnancy tests) will be followed up for clinical and ongoing pregnancy at 2 additional study visits.

Clinical pregnancy will be based on detection of intrauterine gestational sac and/or fetal heart movement on TVUS at approximately 4-5 weeks post-blastocyst transfer. Ongoing pregnancy will be based on detection of at least 1 intrauterine viable fetus at 10-11 weeks gestation (8-9 weeks after blastocyst transfer).

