8.3 Pregnancy and Pregnancy Outcome

Subjects who achieve pregnancy (2 positive β -hCG tests) will be followed for clinical pregnancy (intrauterine gestational sac and/or fetal heart movement approximately 4-5 weeks after embryo transfer) and ongoing pregnancy (approximately 8-9 weeks after embryo transfer). Pregnant subjects will complete their final study visit approximately 8-9 weeks after embryo transfer (or sooner, if there is a loss of pregnancy). Subjects with ongoing pregnancy will be followed by telephone or mail for live birth data and information will be recorded in the eCRF. Pregnancy loss will be recorded on a pregnancy follow-up form in the eCRF.

Trial Code: 000205 Date: 10 Dec 2015 E-Protocol Amendment-19588; Ver. 1.0

Supersedes: 28 October 2015 Page 47 of 69

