9.6.4 Post-Trial Endpoints

All post-trial endpoints will be summarized using tables and figures, as appropriate. Additional details will be specified in the separate Statistical Analysis Plan for the post-trial endpoints. The post-trial endpoints include:

- Cumulative live birth rate for fresh and frozen blastocyst transfer (defined as the proportion of subjects with at least 1 viable live birth greater >21 weeks gestation).
- Live birth rate for fresh blastocyst transfer (defined as the proportion of subjects with at least 1 viable live birth greater >21 weeks gestation).
- Early pregnancy loss rate in frozen blastocyst transfer is defined as 2 positive β-hCG tests but no ongoing pregnancy at 10-11 weeks gestation in the frozen cycle.
- Late pregnancy loss rate (defined as a confirmed ongoing pregnancy but no viable live birth greater >21 weeks gestation).
- Positive β-hCG rate, clinical pregnancy rate, and ongoing pregnancy rate for frozen blastocyst transfers.

Descriptive statistics will be provided in each of the respective post-trial endpoints.

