STATISTICAL ANALYSIS PLAN

A Randomized, Assessor-blind Trial Comparing MENOPUR® (menotropins for injection) and Recombinant FSH (Follicle Stimulating Hormone) in a GnRH Antagonist Cycle with Single-Blastocyst Transfer in a High Responder Subject Population

000205

Investigational Product:	MENOPUR® (menotropins for injection)
Indication:	Development of multiple follicles and pregnancy in ovulatory women as part of an Assisted Reproductive Technology (ART) Cycle with ICSI
Phase:	4
Author:	[name]
Date of issue:	March 8, 2017
Version:	4.0

The information in this document is confidential and is proprietary to Ferring Pharmaceuticals A/S or another company within the Ferring Group. It is understood that information in this document shall not be disclosed to any third party, in any form, without prior written consent of an authorised officer of Ferring Pharmaceuticals A/S or another company within the Ferring Group

Change log

Version No.	Effective Date	Reason for the Change / Revision	Supersedes

2.0	21SEP2015	SAP based on Protocol dated 22JUL2015	Version 1
3.0	16Feb2017	
For some baseline characteristics the analysis based on the safety population has been removed. The summaries based on the mITT and PP populations were considered to be sufficient.For the primary analysis, the sensitivity analysis based on ITT population was removed. Furthermore, sub-group analysis by genetic testing was added.Clarification on protocol deviation analysis.Added forest plots and boxplots.Removed the logistic regression.Other minor clarification and corrections were made.	Version 2
4.0		
In the conduct of the study, it was observed that there were a number of patients that had their primary endpoint visit too early (up to 4 weeks early). Initially, it was planned to use the visit assessment for this analysis however, because of this observation visit windows were considered to be a more accurate assessment for the endpoint. In Section 9, the visit window has now been defined. Furthermore, if a patient has pregnancy assessment beyond this visit she will also be considered as responder.
 
To make it consistent, this type of window was also applied to the clinical pregnancy endpoint.
	Version 3

Author, Reviewers, and Approver of the Statistical Analysis Plan

Author: [name].
Senior Project Statistician, Biometrics
Ferring International Pharmascience Center US, Inc.

Reviewers: [name].
Vice President, Reproductive Health & Urology

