$\hat{\pi}_{Gonal-f}$: is the observed ongoing pregnancy rate of subjects randomized to Gonal-f® in a single fresh treatment cycle following a GnRH antagonist protocol.

$N_{MENOPUR}$: is the number of subjects randomized to MENOPUR®.

$N_{Gonal-f}$: is the number of subjects randomized to Gonal-f®.

$Z_{(1-\alpha/2)}$: is the 1- $\alpha/2$ percentile in the standard normal distribution.

α : is the significance level, i.e., 0.05.

Subjects who do not have at least 1 intrauterine pregnancy with a detectable fetal heartbeat at 10–11 weeks gestation (8-9 weeks after blastocyst transfer in the fresh cycle) due to missing data, early withdrawal, or any other reason will be considered treatment failures (i.e., not having ongoing pregnancy) unless they have an assessment of detectable fetal heartbeat at a later date. Hence, for the analysis of this endpoint all positive (detectable fetal heartbeat) ultrasound assessments that occur in the interval from the end of 7th week from fresh transfer till the end of study will be considered as responder for the primary endpoint (i.e., ultrasound assessment date – fresh transfer date + 1 \geq 7 *7 = 49). Forty nine days was used because the 8-9 weeks visit window included 50

(beginning of the 8th week) to 63 days after fresh transfer. The primary endpoint analysis will be based on the mITT analysis set.

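### Delivery follow-up is required only after ongoing pregnancy is confirmed, so the live birth of a pregnant woman without a confirming scan may go uncollected

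*Protocol*

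**What the plan says.** **Collection.** Four protocol sections tie delivery data to ongoing pregnancy. Section 6.9, on what must be gathered about the delivery, reads "After confirmation of ongoing pregnancy in the fresh cycle or the 6-month post-treatment frozen-thawed blastocyst transfer cycle, the site will be required to collect". Section 8.3 reads "Subjects with ongoing pregnancy will be followed by telephone or mail for live birth data". Section 3.1.2 speaks of delivery information "which will be collected for all subjects with an ongoing pregnancy in the fresh cycle" or in a frozen cycle, and 3.3.7 repeats this. Section 7.1.1 bases ongoing pregnancy on "detection of at least 1 intrauterine viable fetus at 10-11 weeks gestation (8-9 weeks after blastocyst transfer").

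**Endpoint.** Live birth is a secondary objective (Protocol 2.1, SAP 2.1), although its endpoints are listed as post-trial. Protocol 9.6.4 has "Live birth rate for fresh blastocyst transfer (defined as the proportion of subjects with at least 1 viable live birth" beyond 21 weeks, and defines the cumulative rate in the same way. Neither is conditional on ongoing pregnancy. Protocol 9.6.1 assigns post-trial efficacy analyses to the mITT set. Protocol 9 and 9.6.4 leave the details to a separate SAP, which is not among the documents.

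**Scan timing.** The SAP change log for version 4.0 reports that "there were a number of patients that had their primary endpoint visit too early (up to 4 weeks early"). SAP 9.2 then counts as ongoing any positive ultrasound assessments "that occur in the interval from the end of 7th week from fresh transfer till the end of study", that is, from day 49 with the transfer as day 1.

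**The concern.** The endpoint covers all treated women, but collection covers only those whose pregnancy passed one scan-dependent step. A woman may have two positive β-hCG tests, or a heartbeat at Visit 8, and then miss Visit 9, move to obstetric care, or have only an early scan that the site did not treat as ongoing. If she delivers, no section requires anyone to ask.

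What is at stake is the completeness of the fresh and cumulative live-birth rates. A rule in the post-trial SAP can say how to count an unknown outcome, but it cannot recover an outcome that was not collected. The same contact also gathers neonatal health data. In addition, a delivery record would show that a woman without a qualifying scan, who counts as a failure under SAP 9.2 and can fit the early-pregnancy-loss definition in SAP 9.3.3, had in fact carried on.

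**Working it through.** **1. The plan's own figure.** No design figure is given for live birth. The only one is the primary sample size (Protocol 9.1: 50% in both arms, 12-point margin, 1-sided 0.025, 80% power, 8% allowance).

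- n per arm = (1.960 + 0.842)² × (0.25 + 0.25) / 0.12² = 272.5, so 273 against the stated 275.
- Power at 275: 0.12 / √(0.5/275) − 1.960 = 0.854, giving 80.4%.
- 275 / 0.92 = 298.9, so 299 per arm and 598 in all, against about 600.

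The figure reproduces, and the present point does not affect it.

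**2. Who falls outside required follow-up.**

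| Woman's record | Ongoing? | Delivery data required? |
|---|---|---|
| Heartbeat at Visit 9, in window | Yes | Yes |
| Heartbeat on any scan from day 49, including a late one | Yes under SAP 9.2 | Yes, if the site also took it as confirmation |
| Only a scan before day 49 | No under SAP 9.2; the site may have taken it as ongoing | Depends on the site |
| Heartbeat at Visit 8, no later scan | Not confirmed | No |
| Two positive β-hCG tests, no later scan, no documented loss | Not confirmed | No |

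A Visit 9 scan done 4 weeks early falls 4-5 weeks after transfer, which is Visit 8 timing. At the latest it falls 35 days after transfer, or day 36 on the SAP count, short of day 49.

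**3. Size in each arm.** Inputs are 300 per arm and the planned 50% rate. Assumptions are that every continuing pregnancy ends in a live birth (an upper bound) and that 2-5% of the women concerned have no delivery outcome collected.

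- Pregnancies: 300 × 0.50 = 150.
- Births missed: 150 × 0.02 = 3, up to 150 × 0.05 = 7.5.
- Unknown counted as no birth: 147/300 = 49.0% and 142.5/300 = 47.5%, a shortfall of 1.0 to 2.5 points.
- Unknown left out of the denominator, as the general rule in Protocol 9.6.1 would do: 147/297 = 49.5% and 142.5/292.5 = 48.7%, a shortfall of 0.5 to 1.3 points.
- At an assumed 40% live-birth rate with unknown counted as no birth: 300 × 0.40 × 0.02 to 0.05 = 2.4 to 6.0 births, or 0.8 to 2.0 points.

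One uncollected birth is 100/300 = 0.33 points.

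**4. Effect on the between-arm difference.** If each arm loses the same share f of its births and these count as no birth, the observed difference is (1 − f) times the true one. A true 5 points becomes 4.9 at f = 2% and 4.75 at f = 5%. With equal true rates the difference stays at zero.

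**The case against.** The case against is that the gap is narrow and the harm unproven. Most of its limits stand.

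- A reader might infer that these women are never followed. The documents do not say so. Section 6.9 states when collection is required, and nothing forbids it otherwise. Under Protocol 6.7, data from standard-of-care visits "will not be documented in the eCRF unless it is new or is a change in concomitant medications, pregnancy, or AEs", so pregnancy news can reach the database. That route covers visits to the study center only and requires no delivery data.
- A reader might take every missed or mistimed 8-9 week scan as a lost birth. That is too broad, since SAP 9.2 accepts any heartbeat from day 49 to end of study.
- The change log reports early visits, not absent ones. The window came only with SAP version 4.0 (March 2017), as an analysis rule. Sites may well have treated an early heartbeat as ongoing and begun follow-up. The log therefore does not show that any birth was missed.
- A reader might set the shortfall against the 12-point margin. That margin governs the difference in ongoing pregnancy rates. Live birth has no margin or planned test, only descriptive statistics.
- A reader might infer bias between arms because treatment is open-label. Loss of 2% in one arm and 5% in the other would create 50 × (0.05 − 0.02) = 1.5 points, but no section gives a reason why loss should depend on the gonadotropin used.
- How unknown births are counted is for the unseen post-trial SAP, so understatement by the larger amount cannot be asserted.

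What remains is the requirement itself. A site that follows all four sections to the letter need not learn the outcome of a woman with a live clinical pregnancy and no confirming scan.

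**Conclusion.** The point holds as a gap in required collection. It is a cheap improvement to a secondary objective and not a threat to the primary analysis. On the assumption that 2-5% of about 150 pregnancies per arm are affected, each arm's live-birth rate would be about 1.0-2.5 points too low with unknowns counted as no birth, or about 0.5-1.3 points with unknowns removed. The documents supply neither the number of such women nor a live-birth rate, so these are illustrations. The comparison between arms is hardly affected if loss is equal, and unequal loss is not shown. Cumulative live birth is exposed in the same way, because the trigger also governs the frozen cycles.

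**What to change.** In Protocol 3.1.2, 3.3.7, 6.9 and 8.3, require delivery outcome for all subjects with two positive β-hCG tests in the fresh or a recorded frozen cycle and no documented pregnancy loss, whatever their Visit 9 status. Include a woman whose β-hCG result is missing but whose later scan showed a heartbeat, as SAP 9.3.1 already treats her as positive. Use the existing telephone or mail contact. For women who withdrew, contact depends on continuing consent. Where the outcome has already been missed, retrieve it retrospectively.

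In the post-trial SAP:

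- count a documented live birth from that transfer as a live birth;
- state how an unknown outcome is counted, keeping it apart from a known absence of birth;
- report by arm the number with unknown status.

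The cost is a protocol amendment and a few extra contacts per site. On the assumption above, 6 to 15 women over both arms would be spread across 25-30 centers for the fresh cycle, which is fewer than one per center on average (15/25 = 0.6). No visit, procedure or change in sample size is needed.

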7 TRIAL ASSESSMENTS

7.1 Assessments Related to Endpoints

7.1.1 Pregnancy Tests and Pregnancy Monitoring

Positive β -hCG will be based on the detection of 2 positive β -hCG tests in serum via central laboratory. β -hCG pregnancy tests will be performed for all subjects 10-14 days after blastocyst transfer, with a second test approximately 2 days later, if the first test is positive. If conflicting results are obtained in the first 2 tests, a third test will be performed 2 days after the second test. Subjects who achieve pregnancy (2 positive serum pregnancy tests) will be followed up for clinical and ongoing pregnancy at 2 additional study visits.

Clinical pregnancy will be based on detection of intrauterine gestational sac and/or fetal heart movement on TVUS at approximately 4-5 weeks post-blastocyst transfer. Ongoing pregnancy will be based on detection of at least 1 intrauterine viable fetus at 10-11 weeks gestation (8-9 weeks after blastocyst transfer).

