2.2 Endpoints

Primary Endpoint

• Ongoing pregnancy rate, defined as the presence of at least 1 intrauterine pregnancy with a detectable fetal heartbeat at 10–11 weeks of gestation (8-9 weeks after blastocyst transfer in the fresh cycle).

Secondary Endpoints

- Positive β-hCG rate (2 positive β-hCG tests; the first approximately 10-14 days after blastocyst transfer in the fresh cycle and a second confirmatory test approximately 2 days later).
- Clinical pregnancy rate (transvaginal ultrasound [TVUS] showing at least 1 intrauterine gestational sac with fetal heart beat at 6-7 weeks gestation, 4-5 weeks after blastocyst transfer in the fresh cycle).
- Early pregnancy loss (defined as 2 positive β-hCG tests but no ongoing pregnancy at 10-11 week's gestation in the fresh cycle).

Trial Code: 000205

Date: 10 Dec 2015

E-Protocol Amendment-19588; Ver. 1.0

Supersedes: 28 October 2015

Page 16 of 69

- Follicular development as assessed by TVUS (total number of follicles and number of follicles with a diameter of ≤ 9 mm, 10-11 mm, 12-14 mm, 15-16 mm, and ≥ 17 mm on stimulation Day 6 and the last day of stimulation).
- Endocrine profile:
 - Serum follicle-stimulating hormone (FSH), hCG, luteinizing hormone (LH), androstenedione, total testosterone, dehydroepiandrosterone (DHEA): Day 1, Day 6, and last day of stimulation.
 - Progesterone (P4), estradiol (E2): Day 1, Day 6, last day of stimulation, and Visit 4 (morning following hCG administration).
- Oocytes retrieved metaphase II oocytes, number of oocytes undergoing ICSI, fertilization
 rate, quality of embryos 3 days after oocyte retrieval, and the quality of blastocysts 5 days
 after oocyte retrieval.
- Aneuploidy rate.
- Endometrial assessment by TVUS (endometrial thickness in mm and echogenicity pattern on stimulation Day 6, the last day of stimulation, and at the time of blastocyst transfer in the fresh cycle [transabdominal pelvic ultrasound or TVUS]).

Post-trial Endpoints

- Cumulative live birth rate for fresh and frozen blastocyst transfers (viable live birth >21 weeks gestation).
- Live birth rate for fresh blastocyst transfers (viable live birth >21 weeks gestation).
- Early pregnancy loss rate in frozen blastocyst transfer, defined as 2 positive β-hCG tests but no ongoing pregnancy at 10-11 weeks gestation in the frozen cycle.
- Late pregnancy loss rate (defined as a confirmed ongoing pregnancy but no live birth).

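### Protocol 6.7 and Protocol 7.1.1/8.3 send different women to the primary-endpoint scan, and 7.1.1 and 8.3 define clinical pregnancy more loosely than the endpoint does

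*Protocol*

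**What the plan says.** **Definition of clinical pregnancy.** Protocol 2.2 requires an ultrasound "showing at least 1 intrauterine gestational sac with fetal heart beat at 6-7 weeks gestation". The synopsis, 3.1.2, 3.3.7 and the Visit 8 entry in 6.7 also ask for a sac together with a heartbeat, as do SAP 2.2 and 9.3.2. Protocol 7.1.1 differs: "Clinical pregnancy will be based on detection of intrauterine gestational sac and/or fetal heart movement on TVUS". Protocol 8.3 repeats that form: "intrauterine gestational sac and/or fetal heart movement approximately 4-5 weeks after embryo transfer". Read literally, a sac alone is enough in those two sections, and so is heart movement alone.

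**Entry to the primary-endpoint scan.** For Visit 9, Protocol 6.7 says "Subjects with clinical pregnancy will return to the clinic", and it schedules an End of Trial visit for non-pregnant subjects. Protocol 7.1.1 uses a different entry rule: women with two positive serum tests "will be followed up for clinical and ongoing pregnancy at 2 additional study visits". Section 8.3 also starts from two positive tests and places the final visit at about 8-9 weeks after transfer, or sooner if the pregnancy is lost.

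**Scoring.** SAP 9.2 treats a woman without a documented heartbeat at 10-11 weeks as a failure, unless a heartbeat is documented later. It accepts any positive scan from day 49 after fresh transfer to the end of study. SAP 9.3.3 defines early loss as two positive tests without ongoing pregnancy at 10-11 weeks.

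**The concern.** The two inconsistencies meet in one patient: the woman with two positive tests whose Visit 8 scan shows a sac but no heartbeat. Under 7.1.1 and 8.3 she stays in follow-up on either ground, because she has two positive tests and also meets their looser definition. Under 6.7 she does not have clinical pregnancy, so nothing in that section brings her to Visit 9.

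The ascertainment of the primary outcome for such women therefore depends on which section a site follows. A pregnancy that is viable but never scanned again becomes a failure on the primary endpoint. Protocol 6.9 requires delivery information only after an ongoing pregnancy is confirmed, so she could also drop out of live-birth follow-up.

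**Working it through.** **1. Sections side by side**

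| Place | Clinical pregnancy | Who reaches the ongoing-pregnancy assessment |
|---|---|---|
| Protocol synopsis, 2.2, 3.1.2, 3.3.7 | Sac with heartbeat | No entry rule tied to clinical pregnancy |
| Protocol 6.7 | Sac with heartbeat (Visit 8) | Women with clinical pregnancy; End of Trial for non-pregnant subjects |
| Protocol 7.1.1 | Sac and/or heart movement | Every woman with two positive tests |
| Protocol 8.3 | Sac and/or heart movement | Every woman with two positive tests, unless the pregnancy is lost sooner |
| Protocol Table 1 | Not defined | Visit 9 scan listed without a clinical-pregnancy condition |
| SAP 2.2, 9.3.2 | Sac with heartbeat; 9.3.2 counts detectable heartbeats | Not addressed |

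**2. One woman traced through the rules.** She has two positive tests, and a sac without heartbeat at Visit 8.

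- Protocol 7.1.1 and 8.3: followed to 8-9 weeks after transfer. Her outcome is observed.
- Protocol 6.7: not clinically pregnant, so she can be released.
- SAP 9.2: if she is released, the pregnancy continues and no heartbeat scan is recorded with (scan date − transfer date + 1) ≥ 49, she is a failure.
- SAP 9.3.3: she is then an early loss, provided that endpoint uses the ongoing-pregnancy status derived in 9.2. SAP 9.1.3 says that other secondary endpoints are not imputed, so the SAP should make this explicit.
- SAP 9.3.2: she is a non-responder for clinical pregnancy unless a heartbeat is recorded at a later scan. The looser wording in 7.1.1 does not alter that. Protocol 7.1.3 has sac, fetal pole and heartbeat collected.

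**3. The plan's own figures (Protocol 9.1).** Inputs: 50% in both arms, margin 12 points, one-sided 0.025, 80% power, 8% not eligible for the per-protocol set.

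- n per arm = (1.960 + 0.842)² × (0.25 + 0.25) / 0.12² = 7.849 × 0.50 / 0.0144 = 272.5, so 273. The plan uses 275.
- Power at 275: SE = √(0.50/275) = 0.04264; 0.12/0.04264 − 1.960 = 0.854; Φ(0.854) = 80.4%.
- 275/0.92 = 298.9, so 299 per arm and 598 in total, against about 600 stated.

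All three reproduce. None depends on the definition of clinical pregnancy.

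**4. Size.** One misclassified woman in an arm of 300 is 1/300 = 0.33 percentage points. The documents do not say how many there might be, so the following is illustration only. Assume that 1-5% of randomized women have a sac without heartbeat at Visit 8, that 0-25% of those have a heartbeat at 10-11 weeks, and that all are released and unrecorded.

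- Loss per arm of 300: from 0 to 300 × 0.05 × 0.25 = 3.75 women, or 0 to 1.25 points.
- Equal loss in both arms: power at 275 stays 80.4%.
- Whole loss in the MENOPUR arm, power = Φ[(0.12 − loss)/SE − 1.960]: about 78% with 3% sac-only and 10% later viable (loss 0.003), and about 71% at the extreme corner (loss 0.0125).

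**The case against.** Three stronger readings are tempting, and the documents do not support them.

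- *The clinical pregnancy rate will differ by site.* A reader might infer this from the two definitions. SAP 9.3.2 counts only detectable heartbeats, and Protocol 7.1.3 collects that finding. The rate would vary only if a site-entered status were analysed. Neither document says that it is, and neither rules it out.
- *Pregnancy losses are counted from clinical pregnancy status.* They are not. Early loss starts from two positive tests, and late loss starts from ongoing pregnancy. Early loss is affected only through the missed scan.
- *The SAP change log shows that scans were missed.* Version 4.0 reports primary-endpoint visits up to 4 weeks early. Those women attended the visit. The log says nothing about women released after Visit 8.

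There are also real safeguards. SAP 9.2 accepts a later documented heartbeat, and Protocol 6.7 has sites enter new pregnancy information from routine clinic visits in the eCRF. A continuing pregnancy therefore has a route to being counted. Protocol 7.1.1, 8.3 and Table 1 all point to the wider follow-up, so 6.7 is the outlier.

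These points narrow the concern but do not remove it. Neither safeguard requires a scan for a woman whom 6.7 has released. Equal effect in the two arms cannot be taken for granted either: Protocol 3.3.3 and 5.5 blind ultrasound assessors, embryologists and central laboratory personnel, and do not list the staff who schedule visits. Still, the documents give no reason to expect the loss to fall in one arm, so the one-arm power figures are a bound and not a forecast.

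**Conclusion.** The protocol is wrong as written on two linked points. Sections 7.1.1 and 8.3 contradict the endpoint definition of clinical pregnancy. Section 6.7 contradicts 7.1.1 and 8.3 on who is assessed for the primary endpoint, and this second conflict is the one that matters.

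A false failure needs four things together: no heartbeat at Visit 8, viability later, release under 6.7, and no recorded heartbeat scan from day 49 onward. The number of such women is unknown and probably small. Each moves her arm by 0.33 points (arm of 300). Sample size, margin and stated power are unchanged. The analysed clinical pregnancy rate is unaffected if it is derived from recorded scan findings. The contradiction is certain from the text; any effect on the result rests on the assumed ranges in the working.

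**What to change.** 1. Use the 2.2 wording (intrauterine sac with heartbeat) in Protocol 7.1.1 and 8.3.
2. Reconcile 6.7 with 7.1.1 and 8.3, so that the 10-11 week outcome is collected for every woman with two positive β-hCG tests and no documented loss, whatever Visit 8 showed.
3. State in the SAP that clinical pregnancy is derived from the recorded sac and heartbeat findings and not from a site-entered status, and that early loss uses the ongoing-pregnancy status derived in 9.2, if that is intended.
4. Tabulate by arm the women with two positive tests, no documented loss and no scan from day 49 onward.

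The cost is wording in three protocol sections, a sentence or two in the SAP, one table, and a few extra Visit 9 scans that 7.1.1 already calls for. The protocol plans the last visit for December 2016 and SAP version 4.0 is dated March 8, 2017. If visits were complete by then, items 3 and 4 are the ones still available, and item 4 would show whether the problem occurred.
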